Participants will also complete a demographic, sexual behavior, and drug use questionnaire (Enrollment survey), and physical exam findings will be abstracted from the medical record if appropriate.

For the randomized group, in addition to SOC testing, participants will also be randomized to either undergo HIV VL POC testing (Cepheid GeneXpert HIV-1 Viral Load (Xpert VL; Cepheid, Sunnyvale, CA)) using blood already collected or receive SOC testing only. . Those in the non-randomized group will all undergo the Cepheid GeneXpert HIV-1 Qual test, if resources allow. If resources do not allow, the non-randomized group will undergo all standard HIV diagnostics without the HIV VL POC test. Those with confirmed HIV infection will be referred to their preferred clinician, and to the local Disease Intervention Specialist (DIS) team for linkage to care and partner services. Those with non-reactive/negative test results will be referred to their preferred clinician for consideration of HIV PrEP and prevention counselling.

Participants will receive an HIV VL result from the Johns Hopkins Molecular virology lab within 24 hours (same day) using either a validated FDA approved or a validated result from a research use only test performed in a CLIA-licensed lab. Only the results of FDA-approved testing or validated result from a research use only test performed in a CLIA-approved lab may be shared with participants. We will collect blood and transfer the sample to the Immunology Laboratory at JHH for testing. Participants will be contacted within 1 working day of results being released to clinical staff and referred to HIV prevention or treatment services. For the randomized group, in order to ensure that contact details are up-to-date and to proactively answer any participant questions we will contact participants between the 4- and 12-week visits by telephone, SMS, or email as previously agreed.

At Week 4 Visit (all participants – email and/or telephone call)

Participant: Questionnaires: HIV symptom and care; behavioral survey. Linkage to care information. Change in medication. Results of interval laboratory tests.

Study Team (abstraction from medical record): Participant symptoms, physical exam findings. Linkage to care information. Change in medication. Results of interval laboratory tests.

At Week 12 Visit (participants in randomized group only)

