To maximize recruitment efforts and facilitate access to research to the broadest possible community, we will invite members of the public to consider joining the study. We will target key populations, including PrEP users, MSM, and transgender people through outreach to trusted community-based organizations (CBOs). Information will be made available through social media and more traditional methods, such as posters and flyers. Individuals who contact the study team expressing an interest in the study will be invited to the ICTR CRUs.

Prior to study enrollment, the study team will confirm that people who are recruited via non-clinic venues have a medical provider who can be contacted with the results of positive study laboratory results. If a participant does not have a provider, the study team will confirm that they are willing to be referred to an appropriate provider for care and treatment.

Venue for follow up visits and sample collection

Study participants who are recruited from the non-clinical sites described above will be asked to come to the ICTR-CRUs. Similarly, for those with discordant HIV results (recruited from any location) will attend the CRU, Bartlett Clinic, and BCHD for their follow up visits.

7. Drugs/ Substances/ Devices:

- a. The rationale for choosing the drug and dose or for choosing the device to be used.

In this study, we will be testing performance of point of care (POC) devices, Chembio DPP HIV-Syphilis and OraQuick Advance HIV test, for rapid detection of HIV and Syphilis antibodies. Participants in the intervention (POC) arm will also receive nucleic acid amplification test for HIV viral load quantification using Roche Cobas HIV-1 Realtime PCR test and/or Cepheid GeneXpert HIV-1 viral load test.

We acknowledge in-kind contribution (non-monetary support), as Roche Diagnostics and Cepheid have agreed to provide test kits (cartridges) for this study.

- b. Justification and safety information if FDA approved drugs will be administered for non-FDA approved indications or if doses or routes of administration or participant populations are changed.

NA

- c. Justification and safety information if non-FDA approved drugs without an IND will be administered.

NA

8. Study Statistics:

- a. Primary outcome variable.

Proportion of participants linked either to PrEP or ART

- b. Secondary outcome variables.

Syphilis: linkage to syphilis treatment and time to linkage

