HIV: time to linkage to either PrEP or ART; HIV case identification; proportion of persons with HIV started on ART; proportion of persons with HIV and on ART who are virally suppressed at 12 weeks.

HIV ‘knowledge’ – behavioral change (awareness/risk behavior change) since the time of diagnosis.

- c. Statistical plan including sample size justification and interim data analysis.

With a LTC rate of 30% for known positive ED patients who are not in care and a ballpark estimated LTC rate of 50% in STD patients, this translates into an aggregate LTC rate of 40% (assuming 50% patient enrollment in the ED and 50% in the STD clinics). For the randomized group, assuming that the aggregate LTC rate will increase from 40% to 55% after the intervention (POC VL testing), a total of 173 participants are required to enroll in each arm to have a power of 80% to detect the increase of LTC rate from 40% to 55% with a two-sided significant level of 0.05. Factoring in 15% non-response rate, we will need 204 participants in each arm, respectively.

For the non-randomized group, we will recruit up to 1100 participants for the purpose of testing the performance characteristics of rapid tests for HIV and syphilis against SOC laboratory tests, and to bank biospecimens for future evaluation of new POC assays.

We will first analyze descriptive data to determine the proportion of participants linked either to PrEP or ART and the time to linkage; the proportion HIV positive; the proportion with no prior syphilis history who needed treatment; the proportion in which the treponemal test had no added value; the proportion of patients who would still be in the ED/STD clinic at the time the test resulted (for PrEP or ART provision); the proportion of those testing HIV positive who were started on ART; the proportion of those testing positive and started on ART who were virally suppressed at 12 weeks; and the proportion of those with syphilis who are linked to syphilis treatment. This will

be followed by bivariate analysis to explore the potential association between the independent variable (POC HIV VL test) and other covariates with the outcome variable of interest. Then, we will perform multivariate regression to determine the association between having a POC HIV VL test and linkage to PrEP or ART, with adjustment of covariates and confounders.

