We will perform survival analysis (Cox proportional hazard model) to model the time to linkage to PrEP or ART by study arm with adjustment of covariates and confounders. We will also evaluate the performance of the ChemBio DPP HIV test and OraSure oral-fluid assay by calculating the sensitivity, specificity, positive predictive value (PPV), and negative predictive value (NPV).

d. Early stopping rules

NA

e. Secondary Analyses

- Performance accuracy of ChemBio DPP HIV test and OraSure compared to SOC algorithm for HIV
- Seroconversion sensitivity of ChemBio DPP HIV test and OraSure compared to SOC algorithm for HIV
- Performance accuracy of the DPP syphilis test vs lab-based treponemal test;
- Proportion HIV positive
- Performance accuracy of the POC VL test vs quant and qual Roche VL
- Agreement between HIV VL using plasma derived from remnant blood samples and HIV VL tested on plasma from separation cards compared
- Proportion with no syphilis history who needed treatment;
- Proportion in which the treponemal test had no added value
- Turn-around time of the POC test to determine if the patients would have been in the ED/STI clinic at the time the test result became available for the clinician (PrEP or ART provision)

f. Data Management Plan

Collection: JHU will be responsible for collecting all data for this program. JHU project staff will enroll participants into the study. Participants will complete computer-assisted self-interviews and the data will be stored in an electronic high-security password-

protected environment. Blood and oral fluid samples will be collected and submitted for laboratory analyses. Medical record information, including laboratory results, will be abstracted and linked to the individuals study record. All study data will be deidentified before submission to CDC.

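### The regression for the primary outcome is worded by test received, and nothing in the plan ties it to assigned arm or to the randomised group

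*Combined protocol and SAP*

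**What the plan says.** - **Primary outcome (Section 8a):** "Proportion of participants linked either to PrEP or ART", without saying which participants.
- **Sample size (Section 8c):** stated for the randomised group, "assuming that the aggregate LTC rate will increase from 40% to 55% after the intervention (POC VL testing"), so that "a total of 173 participants are required to enroll in each arm to have a power of 80" per cent "with a two-sided significant level of 0.05". Allowing for 15% non-response gives 204 per arm.
- **Analysis (Section 8c):** descriptive summaries come first, then "bivariate analysis to explore the potential association between the independent variable (POC HIV VL test) and other covariates" with the outcome. After that, "we will perform multivariate regression to determine the association between having a POC HIV VL test and linkage to PrEP or ART", adjusted for covariates and confounders that are not listed. No link function, effect measure, analysis population or covariate-selection rule is given.
- **Time to linkage (Section 8c, secondary outcome):** a Cox model "to model the time to linkage to PrEP or ART by study arm".
- **Non-randomised group:** Section 8c sets it at up to 1,100 people, recruited for test performance and specimen banking. Section 5a says: "Those in the non-randomized group will all undergo the Cepheid GeneXpert HIV-1 Qual test, if resources allow". The next sentence of 5a refers to that assay as the HIV VL POC test. The group includes people already taking daily ART or PrEP, and it has no week-12 visit.
- **Early Withdrawals (end of Section 5):** enrolled people who do not finish every enrolment procedure are removed from the study.
- **What counts as the test:** Section 7a allows the POC arm a Roche Cobas assay, a GeneXpert assay or both. Section 5a also uses a Roche Cobas quantitative RNA assay as the tie-breaker in the standard algorithm.

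**The concern.** Randomisation protects a comparison of the groups as assigned. It does not protect a comparison of those who had a test with those who did not, because the reasons for missing a test (leaving early, declining, a failed sample) may also predict failure to link. The plan names study arm for a secondary outcome and a test received for the primary one, and no general as-randomised rule settles the difference.

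The population is open in the same way. A non-randomised person who had the Qual assay can meet the exposure definition as written. Someone already on ART or PrEP may be recorded as linked for reasons unrelated to the test.

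The removal rule adds a third route. If a POC-arm participant who missed the test counts as not having completed enrolment procedures, that person leaves the analysis after randomisation, and the control arm has no matching step.

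With the covariates also left open, the primary estimate could come from several different models.

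**Working it through.** **1. The plan's own figure.** Inputs from Section 8c: 40% vs 55%, two-sided 0.05, 80% power, 1:1. Mean proportion 0.475.

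n = [1.960·√(2·0.475·0.525) + 0.842·√(0.40·0.60 + 0.55·0.45)]² / 0.15² = 172.8, so 173 per arm. 173/0.85 = 203.5, so 204. Both figures reproduce. They are for an unadjusted contrast of two randomised arms.

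**2. Grouping by test received, randomised group only.** The documents give no rate of missed tests and no linkage rate among the untested, so both are assumptions. Let true linkage be 40% in both arms of 204, let a share x of the POC arm be untested and link at rate q, and count them as unexposed.

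Tested = (0.40 − xq)/(1 − x); unexposed = (0.40 + xq)/(1 + x).

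Rejection is for a crude two-sided 5% test of two proportions.

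| x | q | Tested | Unexposed | Difference (points) | Rejection |
|---|---|---|---|---|---|
| 5% | 30% | 40.5% | 39.5% | 1.0 | 5.5% |
| 10% | 30% | 41.1% | 39.1% | 2.0 | 7.0% |
| 10% | 10% | 43.3% | 37.3% | 6.1 | 23.8% |
| 20% | 30% | 42.5% | 38.3% | 4.2 | 13.5% |
| 20% | 10% | 47.5% | 35.0% | 12.5 | 71.4% |

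At q = 40% both expressions equal 40% and there is no bias.

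**3. The same people removed instead of reclassified.** The control arm stays at 40%, so the spurious difference is (0.40 − xq)/(1 − x) − 0.40:
- x = 5%, q = 30%: 0.385/0.95 − 0.40 = 0.5 points
- x = 10%, q = 10%: 0.39/0.90 − 0.40 = 3.3 points
- x = 20%, q = 10%: 0.38/0.80 − 0.40 = 7.5 points

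**4. Pooling the non-randomised group as tested.** Assume all 1,100 are tested and link at rate r, with no true effect. Tested = (204·0.40 + 1100·r)/1304, against 40% in 204 controls, compared crudely.

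| r | Tested | Difference (points) | Rejection |
|---|---|---|---|
| 30% | 31.6% | −8.4 | 66% |
| 40% | 40.0% | 0 | 5% |
| 50% | 48.4% | +8.4 | 61% |
| 60% | 56.9% | +16.9 | 99.5% |

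With 550 tested and pooled, r = 30%, 50% and 60% give −7.3, +7.3 and +14.6 points. If the 1,100 go untested and are pooled as unexposed, the signs in the table reverse. Pooling can also hide a real effect: with true linkage of 40% vs 55% and r = 40%, tested = (204·0.55 + 1100·0.40)/1304 = 42.3%, which turns 15 points into 2.3.

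**5. Covariate selection.** In a simulation of 2,000 null trials (173 per arm, 10 baseline covariates of which 3 were prognostic, kept at p < 0.20 against the outcome), type I error was 5.4% with screening and 5.1% unadjusted. Reporting the smallest p-value of three models (unadjusted, screened, all covariates) gave 7.3%.

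**6. Power under an as-randomised analysis.** 80.0% with 173 evaluable per arm and 86.1% with all 204. If all 204 are analysed and an assumed 15% per arm count as not linked, the rates are 0.40·0.85 = 34.0% and 0.55·0.85 = 46.75%, and power is 74.9%.

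**The case against.** The strongest reply is that the wording is shorthand. The sample-size text equates the intervention with POC VL testing, the Randomization and Blinding text describes the arms by the test, and the Cox model uses study arm. That is plausible, and a reader who infers that the plan has chosen an as-treated analysis goes further than the documents do. What stands is that no sentence confirms the shorthand.

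A reader might also infer that the 1,100 will be pooled. The documents do not plan this. The power calculation is for the randomised group, the other group has a different stated purpose and shorter follow-up, and 5a assigns it the Qual assay where the randomised arm gets the Viral Load assay. Pooling is merely not excluded.

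A third tempting reading is that covariates are screened on the outcome and that this spoils the primary p-value. No selection rule is stated, and the simulation shows that screening alone makes little difference. The point that survives is the lack of prespecification. The bivariate step, read by arm, also contains the crude contrast that was powered, so it should not simply be deleted.

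Finally, the POC VL assay uses blood already collected, which should limit non-receipt, and the removal rule suggests that some untested people would be dropped and not moved across. Both are fair. They favour step 3 over step 2 of the working, with smaller bias but still a loss of people after randomisation.

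**Conclusion.** The concern holds as an omission that governs the primary result. The plan permits an analysis by test received, does not limit the regression to the randomised group, allows removal after randomisation, and names no adjustment covariates. It does not follow that the trial will give an observational answer to a randomised question; the documents only leave that possible.

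The size cannot be fixed from the documents. Under a true null of 40% and the assumed rates, the spurious difference runs from 1.0 to 12.5 points by test received (false positives 5.5% to 71%) and from −8.4 to +16.9 points if all 1,100 were pooled as tested, with zero in between. These are crude comparisons; adjustment might reduce them by an unknown amount. Against a design effect of 15 points, the upper ends could imitate or mask the result. The stated sample size is correct for the comparison that should be made.

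**What to change.** In Section 8c:
- State that the primary analysis compares linkage by assigned arm among all randomised participants.
- State that the non-randomised group enters no arm comparison.
- Keep the unadjusted arm contrast, since that is what was powered, and name the effect measure. A risk difference with a 95% confidence interval is one suitable choice.
- For the adjusted analysis, replace covariates chosen after the bivariate step with a short list fixed in advance from data already collected. Recruitment setting is a natural candidate, since the plan itself assumes 30% linkage in the ED and 50% in STD clinics. Baseline HIV status, taken from the reference algorithm that both arms undergo, is another.
- State how missing linkage is handled, noting the 74.9% power if an assumed 15% count as not linked.
- Keep any analysis by test received as a labelled sensitivity analysis, with the qualifying assays defined.

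In Section 5, reconcile the Early Withdrawals rule with this, so that nobody is removed from the analysis after randomisation for not having received the test.

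The cost is wording in two sections. No new data are needed, and the 173 and 204 per arm do not change.
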